8.5. Special Safety Topics, including Adverse Events of Special Interest

In addition to general safety parameters, safety information on specific topics of special interest will also be presented. Additional special safety topics may be added as warranted. The topics outlined in this section include the protocol-specified adverse events of special interest (AESI).

In general, for topics regarding safety in special groups and circumstances, patient profiles and/or patient listings, where applicable, will be provided, when needed, to allow for medical review of the time course of cases/events, related parameters, patient demographics, study drug treatment, and meaningful concomitant medication use. In addition to the safety topics for which provision or review of patient data are specified, these will be provided when summary data are insufficient to permit adequate understanding of the safety topic.

The analysis and summary will be provided for each treatment period with the corresponding population, where the detailed definition of the population and baseline can be found in Section 8 and [Table JAHW.8.1](#).

8.5.1. Abnormal Hepatic Tests

Hepatic labs include alanine aminotransferase (ALT), aspartate transaminase (AST), total bilirubin (TBL), and serum alkaline phosphatase (ALP). When criteria are met for subgrotic evaluations, investigators will complete a follow-up hepatic safety eCRF. The planned summaries are provided in [Table JAHW.8.6](#).

Table JAHW.8.6. Summary Tables Related to Hepatic Safety

Analysis	Population or Analysis Sets ^a
ALT and AST: The percentages of patients with a measurement greater than or equal to 3 times (3X), 5 times (5X), and 10 times (10X) the central lab ULN for all patients with a post-baseline value and for subsets based on various levels of baseline value.	A, L
TBL: The percentages of patients with a measurement greater than or equal to 2 times (2X) the central lab ULN will be summarized for all patients with a post-baseline value and for subsets based on various levels of baseline value.	A, L
ALP: The percentages of patients with a measurement greater than or equal to 1.5 times (1.5X) the central lab ULN will be summarized for all patients with a post-baseline value and for subsets based on various levels of baseline value.	A, L
Plot of maximum post-baseline ALT vs. maximum post-baseline total bilirubin.	Safety population
Patient profiles including demographics, disposition, information collected on the hepatic-safety CRF (where applicable) and a display of study drug exposure, adverse events, medications, blood pressure, heart rate, and the liver-related measurements over time will be provided for patients with information collected on the hepatic-safety CRF and any additional patients meeting ALT or AST measurement greater than or equal to 5X ULN (on a single measurement) or ALP measurement greater than or equal to 2X ULN (on a single measurement).	Safety population

Abbreviations: ALP = alkaline phosphatase; ALT = alanine aminotransferase; AST = aspartate transaminase; CRF = case report form; TBL = total bilirubin; ULN = upper limit of normal.

^a Analysis Sets are abbreviated as follows: A = Part A safety population, L = Long-term.

8.5.2. Hematologic Changes

Hematologic changes will be defined based on clinical laboratory assessments. Common Terminology Criteria for Adverse Events (CTCAEs) will be applied for laboratory tests potentially related to myelosuppressive events. The planned summaries are provided in [Table JAHW.8.7.](#) and are described more fully in compound-level safety standards.

Table JAHW.8.7. Summary Tables Related to Hematologic Changes

Analysis	Population or Analysis Set ^a
Shift tables showing the number and percentage of patients based on baseline to maximum will be created, with baseline depicted by the most extreme CTCAE grade during the baseline period. With each shift table, a summary displaying the number and percentage of patients who decreased, increased, or stayed the same in CTCAE grade category will be presented.	A, L
The percentages of patients with treatment-emergent shifts at any time will be summarized, based on any increase to CTCAE Grade 1 or above, Grade 2 or above, Grade 3 or above, and Grade 4 or above.	A, L
The percentages of patients with treatment-emergent thrombocytosis will be summarized, defined as an increase in platelet count from a maximum baseline value \leq 600 billion/L to any postbaseline value $>$ 600 billion/L.	A, L

Abbreviations: CTCAE = Common Terminology Criteria for Adverse Events.

^a Analysis Sets are abbreviated as follows: A = Part A safety population, L = Long-term.

8.5.3. Lipids Effects

Lipids effects will be assessed through analysis of elevated total cholesterol, elevated low-density lipoprotein (LDL) cholesterol, decreased and increased high-density lipoprotein (HDL) cholesterol, and elevated triglycerides. The planned summaries are provided in [Table JAHW.8.8.](#) and are described more fully in compound-level safety standards.

Table JAHW.8.8. Summary Tables Related to Lipids Effects

Analysis	Population or Analysis Set ^a
Shift tables showing the number and percentage of patients based on baseline to maximum will be created, with baseline depicted by the most extreme NCEP-based level during the baseline period. With each shift table, a summary displaying the number and percentage of patients who decreased, increased, or stayed the same in NCEP-based level will be presented.	A, L
The percentages of patients with treatment-emergent shifts at any time will be summarized, based on increases to various levels of NCEP-based categories.	A, L
The percentages of patients with treatment-emergent potential hyperlipidemia will be summarized using a predefined MedDRA list of PTs that is a subset of the narrow scope PTs in the MedDRA SMQ “Dyslipidemia.”	A, L

Abbreviations: MedDRA = Medical Dictionary for Regulatory Activities;

NCEP = National Cholesterol Education Program; PT = Preferred Term; SMQ = Standardised MedDRA Query.

^a Analysis Sets are abbreviated as follows: A = Part A safety population, L = Long-term.

Categorical analyses will be performed using Expert Panel on Integrated Guidelines for Cardiovascular Health and Risk Reduction in Children and Adolescents (2011) as shown in [Table JAHW.8.9.](#)

Table JAHW.8.9. Acceptable, Borderline-High, and High Plasma Lipid, Lipoprotein, and Apolipoprotein Concentrations for Children and Adolescents

Category	Low (mg per dL) ^a	Acceptable (mg per dL)	Borderline-high (mg per dL) ^a	High (mg per dL) ^a
total cholesterol	--	<170	170 to 199	≥200
LDL cholesterol		<110	110 to 129	≥130
Non-HDL cholesterol		<120	120 to 144	≥145
Apolipoprotein B		<90	90 to 109	≥110
Triglycerides				
0 to 9 years of age		<75	75 to 99	≥100
10 to 19 years of age		<90	90 to 129	≥130
HDL Cholesterol	<40	>45	40 to 45	
Apolipoprotein A-1	<115	>120	115 to 120	

Abbreviations: HDL = high-density lipoprotein; LDL = low-density lipoprotein.

^a Low cut point for HDL cholesterol and apolipoprotein A-1 represent approximately the 10th percentile. The cut points for high and borderline-high represent approximately the 95th and 75th percentiles, respectively.

8.5.4. Renal Function Effects

Effects on renal function will be assessed through analysis of elevated creatinine. The planned summaries are provided in [Table JAHW.8.10.](#) and are described more fully in compound-level safety standards.

Table JAHW.8.10. Summary Tables Related to Effects on Renal Function

Analysis	Population or Analysis Sets
Shift tables showing the number and percentage of patients based on baseline to maximum will be created, with baseline depicted by the most extreme CTCAE grade during the baseline period. With each shift table, a summary displaying the number and percentage of patients who decreased, increased, or stayed the same in CTCAE grade category will be presented.	A, L
The percentages of patients with treatment-emergent shifts at any time will be summarized, based on any increase to CTCAE Grade 1 or above, Grade 2 or above, Grade 3 or above, and Grade 4 or above.	A, L

Abbreviations: CTCAE = Common Terminology Criteria for Adverse Events.

^a Analysis Sets are abbreviated as follows: A = Part A safety population, L = Long-term.

8.5.5. *Elevations in Creatine Phosphokinase (CPK)*

The planned summaries are provided in [Table JAHW.8.11](#), and are described more fully in compound-level safety standards.

Table JAHW.8.11. Summary Tables Related to Effects on CPK

Analysis	Population or Analysis Set ^a
Shift tables showing the number and percentage of patients based on baseline to maximum will be created, with baseline depicted by the most extreme CTCAE grade during the baseline period. With each shift table, a summary displaying the number and percentage of patients who decreased, increased, or stayed the same in CTCAE grade category will be presented.	A, L
The percentages of patients with treatment-emergent shifts at any time will be summarized, based on any increase to CTCAE Grade 1 or above, Grade 2 or above, Grade 3 or above, and Grade 4 or above.	A, L
Treatment-emergent adverse events potentially related to muscle symptoms may also be analyzed based on reported AEs. The Muscle Symptoms special search category is a predefined MedDRA search criteria list that contains the narrow scope terms from the Rhabdomyolysis/myopathy SMQ plus selected terms from the Musculoskeletal SOC	A, L

Abbreviations: AE = adverse event; CPK = creatine phosphokinase;

CTCAE = Common Terminology Criteria for Adverse Events;

MedDRA = Medical Dictionary for Regulatory Activities; SOC = System Organ Class.

^a Analysis Sets are abbreviated as follows: A = Part A safety population, L=Long-term.

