- h Applicable for sites in Germany only.
- k Performed locally. To be drawn prior to dosing early in the visit.
- l For patients who are positive for HBcAb, a follow-up test for HBV DNA is required. Patients with a positive HBcAb will return to the site and have an HBV DNA sample drawn, which will be processed centrally. Results must be known prior to enrollment. Any enrolled patient who is HBcAb positive, regardless of HBsAb status or level, must undergo HBV DNA testing per the schedule of activities.
- m Urine pregnancy tests are required for females ≥ 10 years of age (<10 years at investigator discretion) if menarche reached or if there is reason to believe the patient is sexually active.
- n Clinical chemistry will include eGFR (calculated by Bedside Schwartz 2009 formula).
- o Fasting lipid profile: Patients should not eat or drink anything except water for 4-12 hours depending on weight and age as specified below. If a patient attends these visits in a nonfasting state, this will not be considered a protocol violation. Recommended fasting times by age and weight are as follows:
 - Patients ≥ 12 years: fast for 12 hours prior to laboratory test
 - Patients 8 to <12 years and weighing >50 kg: fast for 12 hours prior to laboratory test
 - Patients 8 to <12 years and weighing ≤ 50 kg: fast for 8 hours prior to laboratory test
 - Children <8 years and weighing 25 to ≤ 50 kg: fast for 8 hours prior to laboratory test
 - Children <8 years and weighing 10 to <25 kg: fast for 6 hours prior to laboratory test
 - Children <8 years and weighing <10 kg: fast for 4 hours prior to laboratory test

^p If patients are eligible for vaccination with tetanus, diphtheria, and pertussis (TDaP) and/or pneumococcal conjugate vaccine according to local recommended schedule of vaccination, IgG titers for eligible vaccine will be evaluated at prevaccination, 4 weeks postvaccination, and 12 weeks postvaccination.

^q Estradiol (for females) or testosterone (for males) will be collected for the assessment of pubertal development in patients aged 8 to <18 years.

^r Participants 8 years and older will be assessing their sexual maturity. Once the participant reaches the score 5 in the scale, no further assessments are needed.

Note: Due to blood volume restrictions, some laboratory tests may not be collected. Laboratory samples are recommended to be collected as described in the sponsor-provided weight-based prioritization chart ([Appendix 7](#)).

3. Introduction

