8.1. Discontinuation from Study Treatment

8.1.1. *Temporary Interruption of Investigational Product*

In some circumstances, patients may need to temporarily interrupt treatment as a result of AEs or abnormal laboratory values that may have an unclear relationship to investigational product.

Except in cases of emergency, it is recommended that the investigator consult with Lilly (or its designee) before temporarily interrupting therapy for reasons other than those defined in [Table JAHW.8](#).

For the abnormal laboratory findings and clinical events (regardless of relatedness) listed in [Table JAHW.8](#), specific guidance is provided for temporarily interrupting treatment and when treatment may be restarted. Retest frequency and timing of follow-up laboratory tests to monitor the abnormal finding is at the discretion of the investigator. Investigational product that was temporarily interrupted because of an AE or abnormal laboratory value not specifically covered in [Table JAHW.8](#) may be restarted at the discretion of the investigator.

Table JAHW.8. Criteria for Temporary Interruption of Investigational Product

Hold Investigational Product if the Following Laboratory Test Results or Clinical Events Occur:	Investigational Product May be Resumed When:
WBC count <2000 cells/ μ L (<2.00 x 10 ³ / μ L or <2.00 billion/L)	WBC count \geq 3000 cells/ μ L (\geq 3.00 x 10 ³ / μ L or \geq 3.00 billion/L)
ANC <1000 cells/ μ L (<1.00 x 10 ³ / μ L or <1.00 billion/L)	ANC \geq 1500 cells/ μ L (\geq 1.50 x 10 ³ / μ L or \geq 1.50 billion/L)
Lymphocyte count <500 cells/ μ L (<0.50 x 10 ³ / μ L or <0.50 billion/L)	Lymphocyte count \geq 1000 cells/ μ L (\geq 1.00 x 10 ³ / μ L or \geq 1.00 billion/L)
Platelet count <75,000/ μ L (<75 x 10 ³ / μ L or <75 billion/L)	Platelet count \geq 100,000/ μ L (\geq 100 x 10 ³ / μ L or \geq 100 billion/L)
eGFR <40 mL/min/1.73 m ² (from serum creatinine) for patients with screening eGFR \geq 60 mL/min/1.73 m ²	eGFR \geq 50 mL/min/1.73 m ²
eGFR <30 mL/min/1.73 m ² (from serum creatinine) for patients with screening eGFR \geq 40 to <60 mL/min/1.73 m ²	eGFR \geq 40 mL/min/1.73 m ²
ALT or AST >5 x ULN	ALT and AST return to <2 x ULN, and IP is not considered to be the cause of enzyme elevation
Hemoglobin <8 g/dL (<80.0 g/L)	Hemoglobin \geq 10 g/dL (\geq 100.0 g/L)
Symptomatic herpes zoster	All skin lesions have crusted and are resolving

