Appendix 2. Clinical Laboratory Tests

Hematology^a

Hemoglobin
Hematocrit
Erythrocyte count (RBC)
Absolute reticulocyte count
Mean cell volume
Mean cell hemoglobin
Mean cell hemoglobin concentration
Leukocytes (WBC)
Platelets
Mean platelet volume

Absolute counts of:

Neutrophils, segmented
Neutrophils, juvenile (bands)
Lymphocytes
Monocytes
Eosinophils
Basophils

Urinalysis^{a,d}

Color
Specific gravity
pH
Protein
Glucose
Ketones
Bilirubin
Urobilinogen
Blood
Leukocyte esterase
Nitrite

Lipids^{a,b}

Total cholesterol
Low-density lipoprotein
High-density lipoprotein
Triglycerides

Clinical Chemistry^{a,b}

Serum Concentrations of:
Sodium
Potassium
Total bilirubin
Direct bilirubin
Alkaline phosphatase (ALP)
Alanine aminotransferase (ALT)
Aspartate aminotransferase (AST)
Blood urea nitrogen (BUN)
Creatinine
Uric acid
Calcium
Glucose
Albumin
Total protein
Estimated glomerular filtration rate (eGFR)^c
Creatine phosphokinase (CPK)

Other Tests^a

Hepatitis B Surface antigen (HBsAg)^e
Hepatitis B Core antibody (HBcAb)^e
Hepatitis B Surface antibody (HBsAb)^e
Hepatitis C antibody^{e,f}
HBV DNA^g
Human immunodeficiency virus (HIV)^e
HLA-B27
Thyroid-stimulating hormone (TSH)
Exploratory storage samples (RNA, serum, and plasma)
Pharmacogenetic Sample (DNA)
Pregnancy Test (serum)^h
Pregnancy Test (urine)^h
High sensitivity C-reactive protein (hsCRP)
Rheumatoid factor
QuantiFERON®-TB Gold or T-SPOT®.TBⁱ
Purified protein derivative (PPD)^j
ACPA (Anti-CCP)
ESR (sponsor-provided; assayed by clinical study site)
Iron studies (iron, TIBC and ferritin)
Immunoglobulins (IgG, IgA, and IgM)
Lymphocyte subsets (T, B, NK, and T-cell subsets)^j
Antinuclear antibodies
IGF-1
IGFBP-3
Gonadal hormone (estradiol for females aged 8 to <18 years,

testosterone for males aged 8 to <18 years)

Abbreviations: DNA = deoxyribonucleic acid; ESR = erythrocyte sedimentation rate; HCV = hepatitis C virus; HBV = hepatitis B virus; HLA-B27 = human leukocyte antigen-B27; Ig = immunoglobulin; IGF-1 = insulin-like growth factor-1; IGFBP-3 = insulin-like growth factor-binding protein-3; RBC = red blood cell; RNA = ribonucleic acid; TB = tuberculosis; TIBC = total iron-binding capacity; WBC = white blood cell.

- a Unscheduled or repeat blood chemistry, hematology, and urinalysis panels may be performed at the discretion of the investigator, as needed.

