8.1. Extent of Exposure

Duration of exposure (in days) to study drug will be summarized for each treatment period with corresponding safety population, which is defined in [Table JAHW.8.1](#).

Total patient years (PY) of exposure will be reported for overall duration of exposure. Descriptive statistics (n, mean, SD, minimum, 1st quartile, median, 3rd quartile and maximum) will be provided for patient-days of exposure, and the frequency of patients falling into different

exposure ranges will be summarized. Exposure ranges will generally be reported in weeks using the following as a general guide:

For Part A safety analysis population (see [Table JAHW.8.1](#))

- ≥ 4 weeks, ≥ 8 weeks, ≥ 16 weeks, ≥ 24 weeks
- >0 to <4 weeks, ≥ 4 weeks to <8 weeks, ≥ 8 weeks to <16 weeks, ≥ 16 weeks to <24 weeks

For long-term safety analysis population (see [Table JAHW.8.1](#)):

- Every 24 weeks or semi-annually

Overall exposure will be summarized in total PY which is calculated according to the following formula:

$$PYE = \text{sum of duration of exposure in days (for all patients in treatment group)} / 365.25$$

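### SAP 8.5.4 tabulates renal effects only by creatinine CTCAE grade and names no eGFR summary or cut-off, although every renal rule in the protocol is set on eGFR.

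*SAP*

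**What the plan says.** **SAP.** Section 8.5.4 (Renal Function Effects) names one measure: "Effects on renal function will be assessed through analysis of elevated creatinine". Table JAHW.8.10 has two rows, each for the Part A set (A) and the long-term set (L):

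- "Shift tables showing the number and percentage of patients based on baseline to maximum will be created", with CTCAE grade as the category;
- "The percentages of patients with treatment-emergent shifts at any time will be summarized, based on any increase to CTCAE Grade 1 or above", and likewise for Grades 2, 3 and 4.

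The section adds that these summaries "are described more fully in compound-level safety standards". The SAP mentions neither eGFR nor any eGFR cut-off, and gives neither the CTCAE version nor the source of the ULN.

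**Protocol.** The footnotes to both schedules of activities say: "Clinical chemistry will include eGFR (calculated by Bedside Schwartz 2009 formula". Appendix 2 lists "Estimated glomerular filtration rate (eGFR" among the chemistry analytes, and chemistry is scheduled at every treatment visit. The renal rules are all written on eGFR:

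| Rule | Place in protocol | eGFR (mL/min/1.73 m²) |
|---|---|---|
| Exclusion | 6.2, criterion 45 | <40 |
| Baseline dose reduction | 7.1 and 7.4 | <60 |
| Hold, screening eGFR ≥60 | Table JAHW.8 | <40; resume at ≥50 |
| Hold, screening eGFR ≥40 to <60 | Table JAHW.8 | <30; resume at ≥40 |

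**The concern.** The protocol acts on one renal marker and the SAP tabulates another. Table JAHW.8.10 cannot show how many patients reached a level at which the protocol interrupts treatment, although temporary interruption is a named secondary safety endpoint in both parts. By contrast, the hepatic table (JAHW.8.6) counts ALT or AST at 5 times ULN or more, close to the protocol's hold level of more than 5 times ULN.

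The choice of marker matters more in children. Under a height-based formula, the same creatinine means a different eGFR in a small child and in a tall one, and creatinine rises with height when eGFR is unchanged. Elsewhere the SAP does adapt to age: growth z-scores, age-banded blood pressure and pulse limits, and paediatric lipid cut-points. The renal section states no such adjustment. Adalimumab patients leave at Week 24, so Part B has no concurrent arm against which growth drift could be seen.

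**Working it through.** The plan gives no renal figure to reproduce. The check has two parts: what the tables can show, and how creatinine grades behave under stated assumptions.

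**1. Coverage.** The protocol's cut-offs are 60, 50, 40 and 30. None appears in the SAP. Three other outputs could carry eGFR: the spaghetti plots and the abnormal-findings listing in SAP Table JAHW.8.3, and the change-from-baseline chemistry summaries promised in Protocol 10.3.4.2. As described, none counts patients crossing a cut-off.

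**2. Follow-up.** 24 + 260 = 284 weeks; 284 × 7 / 365.25 = 5.4 years.

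**3. Growth at constant eGFR.** The documents name the Bedside Schwartz formula but do not print it. Assume eGFR = k × height / creatinine. At constant eGFR, creatinine is proportional to height and k cancels. The heights are illustrative.

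| Height gain | Ratio | Creatinine |
|---|---|---|
| 95 to 130 cm | 130/95 = 1.37 | +37% |
| 115 to 147 cm | 147/115 = 1.28 | +28% |
| 138 to 170 cm | 170/138 = 1.23 | +23% |

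An adolescent near final height, or a patient who leaves early, would show much less: a 2% height gain gives +2%. Growth over the 24 weeks of Part A is likewise small, so this mechanism belongs mainly to set L. There, taking the maximum favours the later, taller visits.

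Whether these rises become grades depends on the unstated rule:

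- Any rise above baseline counts: all of them are graded.
- More than 1.5 × baseline is needed: none is graded.
- An age-specific ULN is used: growth alone need not be graded.

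**4. Fixed ULN.** Take k = 0.413 (assumed). Creatinine at eGFR 60 is 0.413 × height / 60:

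- 90 cm: 0.62 mg/dL
- 110 cm: 0.76 mg/dL
- 130 cm: 0.89 mg/dL

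The eGFR at which creatinine just reaches a fixed ULN is 0.413 × height / ULN:

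| Assumed ULN (mg/dL) | 90 cm | 110 cm | 130 cm |
|---|---|---|---|
| 0.5 | 74 | 91 | 107 |
| 0.7 | 53 | 65 | 77 |
| 0.9 | 41 | 50 | 60 |
| 1.1 | 34 | 41 | 49 |

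Where an entry is below 60, a child of that height can fall below 60 while creatinine is still within the limit. At 1.1 mg/dL the 90 cm child can also fall below 40. This depends on height rather than growth, so it applies to set A as well as set L. It disappears if the limit is low enough (0.5 mg/dL in this range).

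**The case against.** The strongest reply has four parts.

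- **Other outputs exist.** eGFR is a chemistry analyte, so Protocol 10.3.4.2 already implies a change-from-baseline summary, and SAP 8.3 gives plots and a listing. SAP 8.5 also allows patient profiles where summaries are insufficient. A reader might infer that eGFR will not be reported at all; the documents do not support that. What stands against the reply is narrower: none of these is specified to count crossings of the protocol's cut-offs, and Table JAHW.8.3 does not list the change-from-baseline summary.
- **Compound-level standards may cover it.** They were not supplied, so an eGFR display there can be neither confirmed nor excluded. The SAP cites them as a fuller description of the summaries it has planned, and those are the creatinine rows.
- **No direction of error is shown.** A reader might infer that growth will appear as renal toxicity. That does not follow: it needs a grading rule in which any rise above baseline counts, and the SAP states no rule. The formula, the constant, the heights and the ULN values above are all assumptions. This part of the objection stands in full.
- **Proportion.** Safety is descriptive, the baricitinib arm is about 20 to 30 patients, and investigators apply the hold rules in real time without this table. A five-category shift table will have sparse cells, and individual plots may be more informative. This is fair, but it is a reason to keep the addition small, not to omit counts on the scale that the protocol uses. Interruptions are to be summarised under Protocol 10.3.4, but no breakdown by renal cause is specified.

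**Conclusion.** The mismatch is real and rests on the documents alone: the SAP's renal tabulation is creatinine grade only, while all the protocol's renal rules are on eGFR that is already collected. It merits a change to the SAP.

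The size and direction of any distortion are not established. Under the assumed formula and heights, growth adds 23% to 37% to creatinine over follow-up, which is graded under one plausible rule and not under others. With a fixed ULN of 0.7 to 1.1 mg/dL, loss of function below 60 could pass ungraded in the smallest children, and with 1.1 mg/dL up to at least 130 cm. The supported statement is that creatinine grades could over-call or under-call renal change, and that the SAP does not settle which. Sample size, the primary analysis and all clinical thresholds are unaffected.

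**What to change.** In SAP 8.5.4 and Table JAHW.8.10, for sets A and L:

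1. Add a shift table of baseline to minimum postbaseline eGFR (Bedside Schwartz), using categories formed by the protocol's existing cut-offs: ≥60, 50 to <60, 40 to <50, 30 to <40 and <30 mL/min/1.73 m².
2. Add the number and percentage of patients with treatment-emergent eGFR <60, and of those with values meeting the existing eGFR hold criteria in Protocol Table JAHW.8, by screening eGFR stratum.
3. Carry into the SAP the change-from-baseline eGFR summary by visit that Protocol 10.3.4.2 already implies.
4. Keep the creatinine grades as supportive, and state the CTCAE version, whether grading is relative to baseline or to ULN, and whether the ULN is age-specific.

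The cutoff of 60 serves here only as a descriptive category; no clinical rule changes. The cost is SAP wording and one or two extra tables from data already collected, some with sparse cells at about 20 to 30 patients.
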